8.4.4 Calculation or derivation of safety variable(s)

Safety and tolerability will be assessed in terms of adverse events (including SAEs and adverse events leading to discontinuation), deaths, laboratory data, and vital signs. These will be collected for all subjects. The number of subjects experiencing each adverse event (based on Medical Dictionary for Regulatory Activities [MedDRA] preferred term) will be summarized by CTCAE grade.

8.4.5 Other significant adverse events

During the evaluation of the adverse event data, an AstraZeneca Representative medically qualified expert will review the list of adverse events that were not reported as an SAE or a discontinuation of olaparib due to an adverse event. Based on the expert's judgment, significant adverse events of particular clinical importance may, after consultation with the Safety Physician, be considered other significant adverse events and reported as such in the CSR. A similar review of laboratory/vital signs/ECG data will be performed for identification of other significant adverse events. Examples of these are marked hematological and other laboratory abnormalities, and certain events that lead to intervention (other than those already classified as serious), dose reduction, or significant additional treatment.

8.5 Methods for statistical analyses

Data will be summarized for all subjects who have received at least 1 dose of olaparib. No statistical tests will be performed; the statistical analyses will be purely descriptive. All analyses will be presented by cohort.

Continuous data will be summarized using descriptive statistics (number of observations, mean, standard deviation, median, minimum, and maximum). Frequencies and percentages

will be used for summarizing categorical (discrete) data. Confidence intervals, when presented, will generally be constructed at the 95% level.

8.5.1 Analysis of the primary variable

The ORR will be presented together with the exact 95% CI according to the Clopper-Pearson method.

8.5.2 Analysis of the secondary variable(s)

The DCR and CA-125 response rate will be presented together with the exact 95% CI according to the Clopper-Pearson method.

Kaplan-Meier plots of PFS will be presented for each cohort of subjects. Summaries of the number and percentage of subjects experiencing a PFS event, and the type of event (progression or death) will be provided along with median PFS and 95% CIs.

The analyses of PFS will be based on Investigator assessment according to RECIST v1.1 guidelines, and using all scans regardless of whether they were scheduled or not. The estimated PFS rates at 6 months, 12 months, and 24 months will be summarized (using the Kaplan-Meier curves) if appropriate.

Other time-to-event endpoints (OS, TTAP, DoR) will be described as for PFS.

The safety analyses will consist of assessment of safety and exposure profiles in terms of adverse events/SAEs, laboratory data/vital signs, and ECG that will be collected for all subjects. Appropriate summaries of laboratory data/vital signs and adverse events/SAEs will be produced for all subjects in the safety analysis set per NCI-CTCAE.

Further details will be provided in the SAP.

8.5.3 Subgroup analysis

Subgroup analyses will not be considered within individual cohorts given the limited sample size.

However, for all subjects in the 2 BRCAwt cohorts (myChoice[®] HRD positive and negative) clinical outcomes will be presented according to HRRm status (HRRm positive versus HRRm negative).

8.5.4 Interim analysis

In each cohort, an informal interim analysis will take place after 15 subjects have had at least 1 radiologic tumor response assessment in the first 6 months of the study. If no responses (CR or PR) are observed in the first 15 subjects in a cohort, in consultation with the Steering Committee, the cohort will be closed to further enrollment. However, if there is at least 1 confirmed objective response in the first 15 subjects, that would justify continuing enrollment up to a maximum of 90 subjects. Enrollment will continue until these interim analyses have been completed and a decision is made by the Study Steering Committee.

Additionally annual updates of relevant study data may be generated for the purpose of reporting at appropriate oncology conferences, as specified in the SAP.

The stopping boundary for the interim futility analysis was determined from the binomial probabilities. With a true ORR of 5%, a cohort would terminate early for futility (no responders observed in the first 15 subjects) with a probability of 0.463, while with true ORRs of 10%, 20%, 40%, and 50%, a cohort would terminate early for futility with probabilities of 0.206, 0.0352, 0.0005, and < 0.0001, respectively.

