3.5 Methods for assigning cohorts

Eligible subjects will be enrolled into 1 of 4 cohorts based upon genetic testing performed by a central laboratory to achieve at least 30 subjects in each cohort:

- Cohort 1: gBRCAm,
- Cohort 2: sBRCAm and germline BRCA wild type,
- Cohort 3: myChoice[®] HRD positive (genomic instability positive) and BRCAwt (no BRCA mutation), or
- Cohort 4: myChoice[®] HRD negative (genomic instability negative) and BRCAwt (no BRCA mutation).

Cohort enrollment rules:

The objective response will be monitored on an ongoing basis for subjects in each cohort. If no responses (CR or PR) are observed in the first 15 subjects in a cohort, in consultation with the Steering Committee, this cohort will be closed to further enrollment. However, if there is at least 1 confirmed objective response in the first 15 subjects, that would justify continuing enrollment up to a maximum of 90 subjects. This stopping rule applies to all cohorts. Enrollment in each cohort will continue while the objective response is being assessed for the futility assessment. The objective response will be assessed as per protocol, i.e., allowing 6 months of follow up.

All eligible subjects will provide a screening blood sample for the Myriad BRACAnalysis CDx[®] analysis and a screening tumor sample for the myChoice[®] HRD analysis. Investigative sites will ship these samples to the central laboratory directly. The testing results will be provided back to the Investigator within approximately 14 to 21 days. The Myriad testing may be submitted in advance of the 28-day screening window if the subject consents to the appropriate pre-screening informed consent form.

Prior to any cohorts being closed to enrollment, subjects may enroll in the study and initiate treatment prior to the Myriad BRACAnalysis CDx[®] and myChoice[®] HRD tests being reported; however, subjects will not be allocated into a cohort until the results are received by the Investigator. Once the test results are received by the Investigator, the subject will be allocated into the appropriate cohort. Once a cohort reaches 90 subjects, the cohort will be closed, and subjects may not initiate treatment until their Myriad BRACAnalysis CDx[®] and myChoice[®] HRD tests are completed, the results are received by the Investigator, and it is confirmed there is an open cohort available for which the subject is eligible.

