4.2.4 Study Visit 7, Day 57, and every 4 weeks onwards

Subsequent on-treatment visits for the active treatment period will take place on Day 1 of a 4-week visit period up to 52 weeks (if not progressed and still on treatment), then on Day 1 of a 12-week visit period relative to date of enrollment until PD (RECIST v1.1). Subsequent on-treatment visits for subjects who remain on treatment post-progression should take place every 12 weeks. Tumor assessment visits will be performed at the end of every 8 weeks (± 1 week) up to 48 weeks, then every 12 weeks (± 1 week) relative to date of enrollment until PD (RECIST v1.1). Subjects will be contacted to assess for survival every 12 weeks following disease progression until death, withdrawal of consent, or study closure. See Section 4.4.

The following procedures will be performed at Visit 7, Day 57 (\pm 3 days) and every 4 weeks onward (i.e., Visit 8 [Day 85], Visit 9 [Day 113], etc.) through the active treatment period:

- Assess functional status using the ECOG performance status scale (see Appendix F);
- Obtain blood sample for hematology/clinical chemistry (see Section 5.2.1 and Table 8);
- Obtain blood sample for disease specific marker (CA-125) (see Section 5.2.1.4 and Table 8);
- Assess tumor (CT or MRI according to RECIST v1.1) (see Section 5.1.1);
- Note: The tumor assessments according to RECIST v1.1 will be performed every 8 weeks (± 1 week) from the first dose of study drug (Visit 2) for 48 weeks, and then every 12 weeks (± 1 week) (relative to the date of enrollment) thereafter until determined by the Investigator according to RECIST v1.1 criteria (including confirmatory RECIST scan).
- Assess and record concomitant medications including blood transfusions;
- Assess subject for adverse events (continuous from time of informed consent); and
- Dispense/return olaparib.

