8.4.2 Primary endpoint

The ORR rate is defined as the percentage of subjects with measurable disease with at least 1 visit response of CR or PR that is confirmed at least 4 weeks later. Data obtained up until progression, or last evaluable assessment in the absence of progression, will be included in the assessment of ORR. However, any CR or PR that occurred after a further anti-cancer therapy was received will not be included in the numerator for the ORR calculation. Subjects lacking valid data to assign a response status will be included in the denominator for the response rate calculation based on the efficacy analysis set.

In the case where a subject has 2 non-consecutive visit responses of PR, then, as long as the time between the 2 visits of PR is greater than 4 weeks and there is no PD between the PR visits, the subject will be defined as a responder. Similarly, if a subject has visit responses of CR, NE, CR, then as long as the time between the 2 visits of CR is greater than 4 weeks, a best response of CR will be assigned.

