9.3 Study timetable and end of the study

All subjects who enrolled and received at least 1 dose of olaparib will be followed for survival. Subjects will be contacted to assess survival every 12 weeks following disease progression until death, withdrawal of consent, or study closure.

A data cut-off for analysis of all primary and secondary endpoints will occur approximately 6 months after the last subject enrolled has commenced study treatment (received at least 1 dose of olaparib). The study will remain open for an additional 12 months after this data cut-off for survival follow-up for applicable subjects. At the end of this additional 12 months of survival follow-up, updated OS and safety analyses will be conducted and the study will be

closed. Subjects are, however, permitted to continue to receive olaparib beyond the closure of the database if, in the opinion of the Investigator, they are continuing to receive benefit from treatment with olaparib. During this time (i.e., the 12 months of survival follow-up), AESIs and SAEs must still be collected and reported until 30 days after the subject finally stops taking olaparib. See Sections 6.3.1, 6.3.1.1, and 6.4 for details of adverse event/SAE reporting.

The anticipated enrollment period is approximately 20 months. The study is expected to start in approximately Q4 2016 and to end by approximately Q1 2020.

The study may be terminated at individual sites if the study procedures are not being performed according to Good Clinical Practice (GCP), or if recruitment is slow. AstraZeneca may also terminate the entire study prematurely if concerns for safety arise within this study or in any other study with olaparib. See Section 3.11.

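### Section 8.5.4 lets the 0-of-15 futility look occur after one scan per subject, while Section 3.5 and the synopsis allow 6 months of follow-up; the printed closing probabilities fit only complete follow-up

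*Protocol*

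**What the plan says.** Section 8.5.4 of the protocol sets an informal interim look in each cohort "after 15 subjects have had at least 1 radiologic tumor response assessment in the first 6 months of the study". Section 3.5, with the same text in the synopsis, describes the same futility decision and adds: "The objective response will be assessed as per protocol, i.e., allowing 6 months of follow up". Section 4 sends the reader to both 3.5 and 8.5.4 for the stopping rules and ranks neither above the other.

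The closing condition is "If no responses (CR or PR) are observed in the first 15 subjects in a cohort, in consultation with the Steering Committee", after which the cohort is to be closed. The continuing condition is "at least 1 confirmed objective response in the first 15 subjects, that would justify continuing enrollment up to a maximum of 90 subjects". Enrollment goes on until the committee has decided.

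For the primary endpoint, Section 8.4.2 counts a subject as a responder on "at least 1 visit response of CR or PR that is confirmed at least 4 weeks later". Scans under Section 4.2.4 "will be performed every 8 weeks (± 1 week) from the first dose of study drug (Visit 2) for 48 weeks".

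Section 8.5.4 then gives operating characteristics. At a true ORR of 5%, "a cohort would terminate early for futility (no responders observed in the first 15 subjects) with a probability of 0.463". At 10%, 20%, 40% and 50% the figures are 0.206, 0.0352, 0.0005 and below 0.0001.

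**The concern.** The protocol fixes the maturity of one decision twice, in two different ways. A subject with the Section 8.5.4 minimum has one post-baseline scan, at about week 8. A subject with 6 months has about three. A response that first appears at week 16 or 24 is invisible at the earlier look, so a cohort can show 0 of 15 while some of those 15 go on to respond. The printed probabilities make no allowance for this.

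The two conditions also leave a gap. Closing needs no CR or PR observed, with no mention of confirmation; continuing needs at least one confirmed response. A cohort whose only responses are still unconfirmed meets neither. At an early look that is a likely state, because a subject scanned once cannot yet have a confirmed response.

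What is at stake is the only prespecified efficacy decision rule in an otherwise descriptive trial. It can end enrollment in a biomarker-defined cohort, and the committee applying it would be relying on error rates that do not belong to the look it was given.

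**Working it through.** **The plan's own figures.** P(0 of 15) = (1 − p)^15:
- 0.95^15 = 0.4633
- 0.90^15 = 0.2059
- 0.80^15 = 0.0352
- 0.60^15 = 0.0005
- 0.50^15 = 0.00003

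All agree with Section 8.5.4. At p = 0.30, which the protocol does not list, 0.70^15 = 0.0047. The formula uses the full ORR for every subject, so it holds only when all 15 have complete response ascertainment.

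**Inputs from the protocol.** "The anticipated enrollment period is approximately 20 months" (Section 9.3). The synopsis sample size text foresees up to 90 subjects in each of cohorts 1, 3 and 4 by the time cohort 2 has 30. Scans are every 8 weeks.

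**Assumptions not in the protocol.** Accrual is even, giving 90/20 = 4.5 a month for a large cohort and 30/20 = 1.5 a month for cohort 2. Of eventual responders, 50% to 70% are first seen at week 8 and the rest at weeks 16 to 24. The favorable end is taken as 70% at week 8 and 30% at week 16. The unfavorable end is 50%, 25% and 25% at weeks 8, 16 and 24.

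**Follow-up when the 15th subject reaches week 8.** Subject i has 8 + (15 − i) × (52/12)/rate weeks. At 4.5 a month the step is 0.963 weeks: subject 6 has 16.7 weeks and subject 7 has 15.7, so 6 of 15 have reached week 16 and none week 24. At 1.5 a month the step is 2.89 weeks: 12 of 15 have reached week 16 and 9 have reached week 24.

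**Chance that no CR or PR is observed (the written closing condition), 4.5 a month.** This is the product over subjects of 1 − p × (share of responses already visible).
- ORR 20%, favorable: 0.86^9 × 0.80^6 = 0.2573 × 0.2621 = 0.067
- ORR 20%, unfavorable: 0.90^9 × 0.85^6 = 0.3874 × 0.3771 = 0.146
- ORR 30%: 0.79^9 × 0.70^6 = 0.014, to 0.85^9 × 0.775^6 = 0.050
- ORR 40%: 0.72^9 × 0.60^6 = 0.002, to 0.80^9 × 0.70^6 = 0.016

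**Same condition, 1.5 a month, ORR 20%.**
- Favorable: 0.86^3 × 0.80^12 = 0.044
- Unfavorable: 0.90^3 × 0.85^3 × 0.80^9 = 0.060

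| True ORR | Full follow-up | Section 8.5.4 minimum, 4.5 a month |
|---|---|---|
| 20% | 0.0352 (stated) | 0.07 to 0.15 |
| 30% | 0.0047 | 0.014 to 0.050 |
| 40% | 0.0005 (stated) | 0.002 to 0.016 |

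**If a confirmed response were needed to avoid closure.** At 4.5 a month only the 6 subjects past week 16 can contribute, and only through week-8 responses. At ORR 20% the chance of none is 0.86^6 = 0.40 to 0.90^6 = 0.53.

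**The phrase about the first 6 months.** On a calendar reading with a first scan at week 8 (1.85 months), cohort 2 has 1.5 × (6 − 1.85) = about 6 scanned subjects by month 6, against 15 needed. On a per-subject reading, the 15th cohort 2 subject enrolls at about month 10, is scanned at about month 11.8 and reaches 6 months of follow-up at about month 16, so the look does occur.

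**The case against.** The strongest reply is that Section 3.5 and the synopsis already instruct that the futility assessment allow 6 months, and that Section 8.5.4 sets only a minimum of one scan. Earlier subjects will usually have more. The look is labeled informal, the Steering Committee must be consulted before closure, and enrollment continues meanwhile. Closure stops accrual only; the primary ORR and its exact interval remain defined. All of this stands, and it limits the harm. It does not tell the committee which trigger applies, and it does not make the printed probabilities right for the earlier one.

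Three stronger readings are tempting and are not supported.

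- A reader might infer that a cohort with ORR 20% would be wrongly closed about half the time (0.40 to 0.53). That is the chance of no confirmed response. The closing sentence does not use the word confirmed, so an unconfirmed PR at week 8 blocks closure as written.
- A reader might infer that cohort 2 can never reach the look. That needs both the calendar reading and even accrual of 1.5 a month. The phrase can also mean each subject's own first 6 months. With a planned Q4 2016 start, a calendar window would already have closed before this version of 10 October 2017, which makes that reading unlikely to be the intended one.
- A reader might infer that subjects lost before a first scan drop out of the 15. The trigger does count scanned subjects, but the decision sentence counts the first 15 in the cohort, and nothing says that early losses are excluded.

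**Conclusion.** The conflict is real and stands in the current text. Followed at its minimum, Section 8.5.4 gives a futility rule without its stated operating characteristics. For a cohort accruing 4.5 a month, the chance of 0 of 15 at ORR 20% is roughly two to four times the stated 0.0352. At ORR 40% it stays below 2%. A slow cohort is little affected, because most of its first 15 subjects have longer follow-up by the time of the look.

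These sizes rest on even accrual and on the assumed timing of first response, neither of which the protocol gives. The contradiction between the sections, and the gap for cohorts with only unconfirmed responses, rest on no assumption. If the phrase in Section 8.5.4 means calendar time, cohort 2 would not be expected to trigger the look. Severity: should-fix.

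**What to change.** In Section 8.5.4, replace the trigger with: *when the first 15 treated subjects allocated to the cohort have each had 6 months of follow-up from first dose, or have earlier progressed, died or withdrawn*. Count all 15 in the denominator. Delete the limit to the first 6 months of the study. Use confirmed response in both the closing and the continuing sentence, in Section 3.5 and the synopsis as well. Appendix G contains a sentence saying that responses need no confirmation, which should be reconciled at the same time.

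This aligns Section 8.5.4 with Section 3.5 and the synopsis. The printed probabilities can then stay, with p understood as the rate of response confirmed by the time of the look; a response first seen at week 24 would be confirmed only after 6 months.

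The change adds no visits and leaves the maximum of 90 per cohort as it is. Its cost is a later decision. At 4.5 a month the look moves from about month 5.2 to month 9.3, by which time about 42 rather than 23 subjects are enrolled. At 1.5 a month it moves from about month 11.8 to month 16, with 24 rather than about 18 enrolled. Section 3.5 already accepts that delay by allowing 6 months while enrollment continues.

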9. STUDY AND DATA MANAGEMENT

9.1 Training of study site personnel

Before the first subject is entered into the study, an AstraZeneca Representative will review and discuss the requirements of the Clinical Study Protocol and related documents with the investigational staff and also train them in any study specific procedures and EDC system utilized.

The Principal Investigator will ensure that appropriate training relevant to the study is given to all of these staff, and that any new information relevant to the performance of this study is forwarded to the staff involved.

The Principal Investigator will maintain a record of all individuals involved in the study (medical, nursing, and other staff).

9.2 Monitoring of the study

During the study, an AstraZeneca Representative will have regular contact with the study site, including visits to:

- Provide information and support to the Investigator(s);
- Confirm that facilities remain acceptable;
- Confirm that the investigational team is adhering to the protocol, that data are being accurately and timely recorded in the eCRFs, that biological

samples are handled in accordance with the laboratory manual, and that study medication accountability checks are being performed;

- Perform source data verification (a comparison of the data in the eCRFs with the subject's medical records at the hospital or practice and other records relevant to the study) including verification of informed consent of participating subjects. This will require direct access to all original records for each subject (e.g., clinic charts); and
- Ensure withdrawal of informed consent to the use of the subject's biological samples is reported and biological samples are identified and disposed of/destroyed accordingly, and the action is documented, and reported to the subject.

The AstraZeneca Representative will be available between visits if the Investigator(s) or other staff at the site needs information and advice about the study conduct.

9.2.1 Source data

Refer to the Clinical Study Agreement for location of source data.

9.2.2 Study agreements

The Principal Investigator at each site should comply with all the terms, conditions, and obligations of the Clinical Study Agreement, or equivalent, for this study. In the event of any inconsistency between this Clinical Study Protocol and the Clinical Study Agreement, the terms of the Clinical Study Protocol shall prevail with respect to the conduct of the study and the treatment of subjects, and in all other respects not relating to study conduct or treatment of subjects, the terms of the Clinical Study Agreement shall prevail.

Agreements between the AstraZeneca Representative and the Principal Investigator should be in place before any study-related procedures can take place, or subjects are enrolled.

9.2.3 Archiving of study documents

The Investigator follows the principles outlined in the Clinical Study Agreement.

9.3 Study timetable and end of the study

All subjects who enrolled and received at least 1 dose of olaparib will be followed for survival. Subjects will be contacted to assess survival every 12 weeks following disease progression until death, withdrawal of consent, or study closure.

A data cut-off for analysis of all primary and secondary endpoints will occur approximately 6 months after the last subject enrolled has commenced study treatment (received at least 1 dose of olaparib). The study will remain open for an additional 12 months after this data cut-off for survival follow-up for applicable subjects. At the end of this additional 12 months of survival follow-up, updated OS and safety analyses will be conducted and the study will be

closed. Subjects are, however, permitted to continue to receive olaparib beyond the closure of the database if, in the opinion of the Investigator, they are continuing to receive benefit from treatment with olaparib. During this time (i.e., the 12 months of survival follow-up), AESIs and SAEs must still be collected and reported until 30 days after the subject finally stops taking olaparib. See Sections 6.3.1, 6.3.1.1, and 6.4 for details of adverse event/SAE reporting.

The anticipated enrollment period is approximately 20 months. The study is expected to start in approximately Q4 2016 and to end by approximately Q1 2020.

The study may be terminated at individual sites if the study procedures are not being performed according to Good Clinical Practice (GCP), or if recruitment is slow. AstraZeneca may also terminate the entire study prematurely if concerns for safety arise within this study or in any other study with olaparib. See Section 3.11.

